8.1.3.1 Intensity

Intensity will be recorded for each reported AE. The following definitions of intensity are to be used:

Mild: Awareness of symptoms or signs, but easily tolerated (acceptable)

Moderate: Enough discomfort to interfere with usual activity (disturbing)

Severe: Incapacity to work or to do usual activity (unacceptable)

If the intensity changes within one day, the maximum intensity of the AE during that day shall be recorded.

8.1.3.2 Causal relationship and seriousness

Each AE shall be assessed by the Investigator for causal relationship with the study product and its use (the injection procedure) and for seriousness (Yes or No) of the event.

A two-point scale (Yes or No response) shall be used for the causality assessments. The Investigators shall be asked to indicate a response to each of the following questions in the eCRF:

- "Do you consider that there is a reasonable possibility that the event may have been caused by the study product?", and
- "Do you consider that there is a reasonable possibility that the event may have been caused by the study product injection procedure?"

If any of these questions is answered Yes, the AE is considered related.

Each AE will also be assessed for causal relationship and seriousness by the Sponsor, in order to fulfil regulatory requirements.

In addition, each SAE will be classified by both the Investigator and the Sponsor separately, according to four different levels of causality:

- Not related Relationship to the device, comparator or procedures can be excluded when:
 - the event has no temporal relationship with the use of the investigational device, or the procedures related to the investigational device;
 - the serious adverse event does not follow a known response pattern to the medical device (if the response pattern is previously known) and is biologically implausible;
 - the discontinuation of medical device application or the reduction of the level of activation/exposure – when clinically feasible – and reintroduction of its use (or increase of the level of activation/exposure), do not impact on the serious adverse event;
 - the event involves a body-site or an organ that cannot be affected by the device or procedure;
 - the serious adverse event can be attributed to another cause (e.g. an underlying or concurrent illness/clinical condition, an effect of another device, drug, treatment or other risk factors);

•	Title 05DF1910 Clinical Study Protocol	Doe id
♣ GALDERMA	•	MA-42248

the event does not depend on a false result given by the investigational device used for diagnosis, when applicable;

In order to establish the non-relatedness, not all the criteria listed above might be met at the same time, depending on the type of device/procedures and the serious adverse event.

- Possible The relationship with the use of the investigational device or comparator, or the relationship with procedures, is weak but cannot be ruled out completely. Alternative causes are also possible (e.g. an underlying or concurrent illness/ clinical condition or/and an effect of another device, drug or treatment). Cases where relatedness cannot be assessed, or no information has been obtained should also be classified as possible.
- 3. **Probable** The relationship with the use of the investigational device or comparator, or the relationship with procedures, seems relevant and/or the event cannot be reasonably explained by another cause.
- 4. Causal relationship the serious adverse event is associated with the investigational device, comparator or with procedures beyond reasonable doubt, when:
 - the event is a known side effect of the product category the device belongs to or of similar devices and procedures;
 - the event has a temporal relationship with investigational device use/application or procedures;
 - the event involves a body-site or organ that
 - the investigational device or procedures are applied to;
 - the investigational device or procedures have an effect on;
 - the serious adverse event follows a known response pattern to the medical device (if the response pattern is previously known);
 - the discontinuation of medical device application (or reduction of the level of activation/exposure) and reintroduction of its use (or increase of the level of activation/exposure), impact on the serious adverse event (when clinically feasible);
 - other possible causes (e.g. an underlying or concurrent illness/ clinical condition or/and an effect of another device, drug or treatment) have been adequately ruled out:
 - harm to the subject is due to error in use;
 - the event depends on a false result given by the investigational device used for diagnosis, when applicable;

In order to establish the relatedness, not all the criteria listed above might be met at the same time, depending on the type of device/procedures and the serious adverse event.

8.1.4 Reporting of adverse events

Adverse event reporting on each subject shall start at baseline (visit 2) after the subject has been randomized. The reporting shall continue during each follow-up visit (including

•	05DF1910 Clinical Study Protocol	Doc id
GALDERMA	•	MA-42248

telephone contacts and extra visits between planned visits) until the last scheduled visit in the study.

All AEs, non-serious as well as serious, are to be reported as an AE in the eCRF.

8.1.5 Reporting of serious adverse events

The Investigator shall report any **SAE** to the Sponsor or via Sponsor's representative, **immediately but not later than 24 hours of awareness of the event**. This initial report can be made via fax or e-mail or submitted via the eCRF.

In case of difficulty to obtain all the required information within 24 hours, an initial report can be submitted, with the following information as a minimum, irrespective of whether some of it is regarded as preliminary:

- Subject identification (age, gender, initials, subject number)
- Adverse event description
- Date when AE occurred
- Name of PI
- · Name of study product

Follow-up information and data missing in the initial SAE reporting shall be gathered as soon as possible and reported to the Sponsor's representative immediately but not later than 24 hours of awareness of the new data. Complete and adequate information on each SAE is required. All attempts to obtain this information, including dates for follow-up activities, must be documented by the Investigator.

Supporting documentation to be provided with the SAE report:

- Concomitant therapies form/list
- AE form/list
- Medical history form/list
- Any other relevant supporting documentation (e.g. hospital notes, death certificate, autopsy reports etc.)

E-mail for SAE reporting: [contact]

Fax number for SAE reporting: [name]

For non urgent complementary information not possible to send by e-mail or fax, please use surface mail.

Surface mail for providing Q-Med AB

complementary information: Attn. Safety - Medical Affairs

[name]

[name]

MA-42248.doc

05DF1910 Clinical Study Protocol 👶 GALDERMA MA-42248

The SAE form must be signed and dated by the Investigator. If the initial 24-hour SAE report does not contain full information or if it is made without using the SAE form the fully completed and signed SAE form shall be e-mailed or faxed to the Sponsor. A copy of the fully completed SAE form shall be kept at the site.

In addition, the PI shall report SAEs to the responsible IEC without undue delay. The PI is responsible for checking what reporting procedures are applicable for his/her IEC regarding SAEs and final report of the outcome of the study and to comply with such reporting procedures during the study period.

The Sponsor is responsible for reporting to the CA, if applicable and according to national regulations. For all SAEs which indicate an imminent risk of death, serious injury, or serious illness and that requires prompt remedial action for other subjects, users or other persons or a new finding to it: immediately, but not later than 2 calendar days after awareness by Sponsor.

For a description of the procedure regarding emergency unblinding, see section 4.4.3.

8.1.6 Follow-up of unresolved events ongoing at termination of the study

All serious as well as non-serious AEs with a causal relationship to the study product or treatment procedure and ongoing at study end, shall be followed up after the subject's participation in the study is over. Such events shall be followed-up after the last study visit until resolved, assessed as chronic or stable, or for three months. Final outcome after the end of the study shall be reported on AE follow up form.

8.1.7 Reporting and follow-up of events occurring after subject termination of the study

All AEs with a causal relationship to the study products or treatment procedure that the Investigator becomes aware of, serious as well as non-serious, with onset after the study termination (subject's last study visit) shall be reported to the Sponsor. The report should as a minimum include the information described in section 8.1.3. The report can be sent via fax or e-mail according to contact details specified in section 8.1.5. The events shall thereafter be followed-up until resolved or considered chronic or stable, or for at least three months. Final outcomes shall be reported.

8.1.8 Pregnancy

Pregnancy itself is not regarded as an AE.

If there is a pregnancy during the study period the subject must be withdrawn from any following study treatment, but should continue to be followed within the study and the outcome of pregnancy must be reported even if the delivery occurs after study completion.

A pregnancy confirmed during the study period must be reported by the Investigator on a pregnancy report form immediately upon acknowledge be submitted to the Sponsor according to contact details specified in section 8.1.5. The report can be prospective or retrospective. Follow-up shall be conducted to obtain outcome information on all prospective reports.

Cases that led to fetal distress, fetal death or a congenital abnormality or birth defect are to be regarded as SAEs and shall be reported on the exposure in utero report form to the Sponsor immediately but no later than 24 hours after the Investigators awareness. These events shall be handled as SAEs during data processing. Other complications during the pregnancy that are related to the pregnant woman and fulfils any serious criteria, such as pre-eclampsia

Print date:

requiring hospitalization, shall be reported and handled as SAEs. Elective abortions without complications shall not be reported as AEs.

8.1.9 Anticipated adverse events

Information regarding anticipated AEs for Restylane Defyne is included in the IFU.

8.2 Device deficiencies

8.2.1 Definition of a device deficiency

A device deficiency is defined as an inadequacy of a medical device with respect to its identity, quality, durability, reliability, safety^{‡‡}, or performance.

Note: Device deficiencies include malfunctions, use errors, and inadequate labelling.

8.2.2 Recording instructions

When a device deficiency is discovered, Part A of the clinical study complaint form shall be completed by the Investigator. The type of complaint shall be described and injury to the subject or user or unintended exposure to study product shall be reported as applicable. If an injury has occurred, an AE module or an SAE form shall be completed as applicable (refer to section 8.1). If no SAE was experienced as a result of the device deficiency the Investigator shall assess whether or not the device deficiency could have led to an SAE if:

- Suitable action had not been taken,
- Intervention had not been made or,
- Circumstances had been less fortunate

In Part B of the clinical study complaint form the Sponsor will make the same assessment.

8.2.3 Reporting of device deficiencies

The Investigator shall send the completed clinical study complaint form to the Sponsor.

E-mail for device deficiencies reporting: [contact]

Fax number for device deficiencies reporting: [name]

A device deficiency that led to a SAE and any device deficiency that could have led to a SAE shall be reported to the Sponsor within 24 hours after the Investigator's awareness (for contact information, see section 8.1.5).

If the Investigator or the Sponsor assesses that the device deficiency could have led to a SAE the Sponsor is responsible for reporting the device deficiency to CA and the PI is responsible for reporting it to the IEC.

Inadequacy of device safety refers to properties of the device which could have or have led to an AE.

The deficient study product shall be kept by the study site until the Sponsor has confirmed whether the product shall be returned to Sponsor for further study or if it can be destroyed at the study site.

Data Handling and Management

Data management

Data management based on GCP refers to the activities defined to achieve safe routines to enter clinical data information into a database, efficiently and avoiding errors. The data management routine includes procedures for database set-up and management, data entry and verification, data validation, and documentation of the performed activities including information of discrepancies in the process. The data management process will be described in detail in the data management plan (DMP).

The database, the data entry screens and program will be designed in accordance with the CSP and the CRF template. Data validation will be performed by computerized logical checks and manual review. Drugs and events will be coded in accordance with World Health Organization (WHO) Drug and medical dictionary for regulatory activities (MedDRA) dictionaries as specified in the DMP. SAE information in the clinical database will be reconciled against the data in the safety database.

When all efforts have been made to ensure that the data recorded in the eCRFs and entered in the database is as correct and complete as possible, the clinical database will be locked. Study data will be transferred to SAS datasets, which thereafter will be write-protected. Statistical analyses will be generated in SAS using data from the locked datasets.

9.2 Electronic case report forms

An electronic data capture application, compliant with regulatory requirements for software validation complying with US FDA 21CFR11 will be used to collect, modify, maintain, archive, retrieve, and transmit study data. An eCRF is required and shall be completed electronically for each screened subject (screening visit) and enrolled subjects (subsequent visits).

The eCRF includes password protection and internal quality checks, such as automatic range checks, to identify data that appear inconsistent, incomplete, or inaccurate. Study data shall be entered directly from the source documents, which are to be defined at each site before inclusion of the first subject.

Authorized study site personnel designated by the PI shall complete data collection. Appropriate training and security measures shall be completed with all authorized investigation site personnel prior to the study being initiated and any data being entered into the system for any subject.

The study data is the sole property of the Sponsor and shall not be made available in any form to third parties, except for authorized representatives of appropriate CA, without written permission from the Sponsor. At the end of the study, electronic data are kept at the Sponsor and a copy (provided by the vendor) at the study site as part of the Investigator file.

Any delegation of collection of data shall be specified and recorded.

Effective date: 2020-10-02 11:10

Doc id

MA-42248

9.2.1 Data entry

All data shall be entered in English. The eCRFs should always reflect the latest observations on the subjects participating in the study. Therefore, the eCRFs shall be completed as soon as possible during or after the subject's visit. The subject's identity must always remain confidential, i.e. the name and address of the subjects must not be registered in the eCRFs or in the database. The Investigator must verify that all data entries in the eCRFs are accurate and correct. If some assessments are not done, or if certain information is not available, not applicable or unknown, the Investigator shall indicate this in the eCRF. The Investigator shall electronically sign off the study data. By signing, the Investigator takes responsibility for the accuracy, completeness, and legibility of the data reported to the Sponsor in the eCRF.

9.2.2 The query process

The monitor shall review the eCRFs and evaluate them for completeness and consistency. Each eCRF shall be compared with the respective source documents to ensure that there are no discrepancies between critical data. All entries, corrections, and alterations shall be made by the PI or his/her authorized designee. The monitor cannot enter data in the eCRFs. Once study data have been submitted to the central server via the eCRF, corrections to the data fields will be audit trailed, meaning that the reason for change, the name of the person who made the change, together with time and date will be logged. Roles and rights of the site personnel responsible for entering study data into the eCRF shall be determined in advance. If discrepant data is detected during review of the data, either by the Sponsor or by its representatives, the responsible data manager or monitor shall raise a query in the electronic data capture application. The query shall state the question or data to be changed and shall be resolved in the system by the PI or his/her authorized designee. The appropriate study site personnel shall answer the queries in the eCRF. This will be audit trailed by the electronic data capture application meaning that the name of study site personnel, time, and date is logged.

9.2.3 User identification

Electronic CRF records will be automatically appended with the identification of the creator, by means of their unique UserID. Specified records shall be electronically signed by the Investigator to document his/her review of the data and acknowledgement that the data are accurate. This will be facilitated by means of the Investigator's unique UserID and password; date and time stamps will be added automatically at time of electronic signature. If an entry in an eCRF requires change, the correction shall be made in accordance with the relevant software procedures.

9.2.4 Audit trail

All changes will be fully recorded in a protected audit trail and a reason for the change shall be stated. Once all data have been entered, verified, and validated, the database will be locked.

9.3 Source documents

The eCRF is essentially considered a data entry form and does not constitute the original (or source) medical records unless otherwise specified. Source documents are all documents used by the Investigator or hospital that relate to the subject's medical history, that verifies the existence of the subject, the inclusion and exclusion criteria, and all records covering the

subject's participation in the study. They include laboratory notes, memoranda, material dispensing records, subject files, etc.

The PI is responsible for maintaining adequate and accurate source documents. Source data should be attributable, legible, contemporaneous, original, accurate, and complete. Changes to source data should be traceable, should not obscure the original entry and should be explained if necessary.

These shall be made available for inspection by the monitor at each monitoring visit. The Investigator must submit a completed eCRF for each subject for whom signed informed consent has been collected. All supportive documentation submitted with the eCRF, such as laboratory or hospital records, shall be clearly identified with the CTN and subject number. Any personal information, including name, shall be removed or rendered illegible to preserve individual confidentiality.

9.4 Record keeping and access to source data

The PI/Institution shall permit study-related monitoring, audits, IEC review, and CA inspections and shall provide direct access to the source data/medical record including the identity of all participating subjects (sufficient information to link records, i.e. eCRF, medical records, original signed ICF and detailed records of study product accountability). The records shall be retained by the PI as required by local legislation and international guidelines. Any transfer of responsibility for storage of the records shall be documented and the Sponsor shall be informed in writing.

The Sponsor shall verify that each subject has consented in writing to direct access to the original medical record/source data (by the use of written subject information and signed informed consent). The data recorded in the eCRFs will be checked for consistency with the source documents/medical record by the monitor during monitoring (source data verification; SDV). In order to be able to perform SDV, information about each subject's participation in the study has to be detailed in the medical record or other relevant source.

Document and data retention

All records pertaining to the conduct of the study, including signed eCRFs, ICF, study product accountability records, source documents, and other study documentation must be retained for 15 years after study completion or longer if required by national legislation. Sponsor will inform the site(s) as to when these documents no longer needs to be retained. Measures shall be taken to prevent accidental or premature destruction of these documents (e.g. protection against damage and unauthorized access, preferably by storage in a fireproof cabinet).

After study completion and database lock, a security sealed CD with electronic study data shall be provided by the eCRF vendor for archiving.

It is the PI's responsibility to inform the Sponsor in writing if the Investigator file is moved or if the responsibility for the documents is transferred to someone else.

10. Statistical Methods

10.1 Analysis populations

The following populations will be defined:

Includes all subjects who were injected with study Safety

product.

Includes all treatment compliant subjects, i.e. subjects Modified Intention-totreated at both baseline and 3 weeks. treat (MITT)

All efficacy analyses will be based on the MITT population. Safety analysis is performed based on the safety population set.

The disposition of subjects will be presented in tables and/or figures as appropriate. The number of screened, treated, completed, and withdrawn subjects will be presented, as well as number of subjects in each analysis population set.

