2.2.1.2 Clinical documentation

The first injectable OBT gel product was CE-marked in Europe in 2009. Several studies have been conducted to assess the safety and efficacy of OBT products in the treatment of e.g. cheeks, NLFs, and lips 6-10.

Study rationale and justification for design 2.3

This study aims to document the results of a stepwise treatment and determine if any of the two approaches to be used in this study, down-up and top-down, affects the studied endpoints. Results from the study will be the basis for future treatment guidelines used by aesthetic health care practitioners when injecting Restylane Defyne in the chin, NLF and ML.

Approximately 60 subjects (of which at least 20 males) will be enrolled and randomized into two groups with different treatment schedules. Comparison between the two groups will help to determine if the different treatment approaches affects the outcome, such as subject satisfaction.

Risks and benefits

After the injection of the study products, some common injection-related reactions might occur. These reactions include erythema, swelling, pain, itching, bruising or tenderness at the implant site. Typically, resolution is spontaneous within a few days after injection.

There is a risk that the subject will not gain the full aesthetic correction of the treated areas. There is also a risk for development of palpable HA lumps or displacement of the injected HA. Inflammation or infection has been reported in a few cases after treatment. There may be risk of bruising and/or damaging body structures such as nerves or blood vessels connected to the injection site, however these risks are minor.

Following facial aesthetic treatments isolated rare cases have been reported regarding ischemic events affecting the eye leading to visual loss, and the brain resulting in cerebral infarction. Detailed information on reported adverse events (AE) relevant for the study product is provided in the instructions for use (IFU).

Lidocaine can in rare cases give allergic reactions, and therefore subjects with known allergy or hypersensitivity to local anaesthetics should not be included in the study.

Given the anticipated low level of transient and acceptable AEs in connection with the injection, the risk-benefit assessment of the use of the study products for lower face augmentation offers a potential clinical benefit, such as subject rated improvement of attractiveness and satisfaction, at reasonable risk.

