3.1 Objectives and endpoints

3.1.1 Effectiveness objectives and endpoints

Objective

Endpoint

and Treating Investigator assessment using the Global Aesthetic Improvement Scale at week 3, 6 and 9.

Objective

To evaluate naturalness of the treatment result

Endpoint

Assessed by and Treating Investigator using directed questions at week 3, 6 and 9.

Objective

To evaluate subject satisfaction treating chin versus treating NLF/ML, respectively, and in combination.

Endpoint

MA-42248.doc

Doc id 05DF1910 Clinical Study Protocol 🚣 GALDERMA MA-42248

Subject assessment using subject satisfaction questionnaire and at baseline, week 3, 6 and 9.

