5.5 Withdrawal of subjects

An investigator may decide to discontinue a subject from the clinical study for safety reasons.

Although the importance of completing the entire clinical study should be explained to the subject by the clinical study personnel, any subject is free to discontinue participation in this clinical study at any time and for whatever reason, specified or unspecified, and without any prejudice. No constraints are to be imposed on the subject, and when appropriate, a subject may be treated with other conventional therapy when clinically indicated.

When a subject does not complete the clinical study, he/she will be fully assessed, if such assessment is possible. The procedures designated for the early termination visit should be completed for all subjects discontinuing the clinical study and the appropriate eCRF should be completed.

All discontinuations and the reason for discontinuation are to be documented by the investigator on the Exit form.

For discontinuation due to and AE, the Adverse Event form is to be completed. The investigator should also ensure that the subject receives suitable therapy for the AE.

A subject who has been randomized and assigned a kit number/randomization number cannot be replaced by another subject if he/she discontinues the clinical study for any reason. Additional subjects could be enrolled (randomized/assigned to treatment) in order to attain the number of evaluable subjects.

Pregnancies occurring during the screening period are considered as screening failures; they should be recorded as such in the eCRF and no pregnancy form is to be completed.

In case of a pregnancy occurring after the baseline visit, follow the procedures described in section 8.1.8. The subject may remain in the study, but no invasive procedure should be conducted.

The Sponsor may also decide to prematurely terminate or suspend a subject's participation in the clinical study.

Potential reasons for discontinuation are defined below:

The withdrawal criteria are:

- Medical reasons: If the subject suffers from a medical condition that in the judgement
 of the Investigator makes it medically necessary to withdraw the subject. The specific
 rationale for Investigator-initiated withdrawal of a subject for medical reasons shall
 document the specific condition for withdrawing the subject.

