7.1 General information

The methods for collecting efficacy data include 2D photography (section 7.2), GAIS (section 7.3), naturalness (7.4), subject satisfaction questionnaire (7.6), and a section 4.7).

At treatment visits, all assessments must be performed before study treatment is administered.

To avoid inter-observer variability, every effort should be made to ensure that the same individual who made the initial screening or baseline determinations completes all corresponding follow-up evaluations.

7.2 2D Photography

Photographs shall be taken prior to the injections of the investigational product when applicable and at follow-up visits in order to document treatment effect.

Note that no covering make-up shall be used on the photographs.

At visits where injections are performed, the photographs shall be taken prior to the injections and should include a front, 45°-front lateral, and profile picture.

Instructions for photography are provided in a separate photography manual. Each photograph shall be labelled with the subject number, and the visit number at which the photograph was taken. In order to maintain confidentiality, the photographs must not include any information that may reveal the subject's identity. The photographs should be used in the assessment of GAIS,

AEs. The photographs shall be presented on a computer monitor (preferably the same monitor throughout the study).

Photographs shall be taken at the time points indicated in the schedule of events (section 4.7).

Doc id 05DF1910 Clinical Study Protocol 👶 GALDERMA MA-42248

Global Aesthetic Improvement Scale (GAIS)

The GAIS is a qualitative 5-graded scale evaluating aesthetic improvement (Table 3). While GAIS is neither an objective measurement tool nor a validated tool, GAIS improvement has been commonly accepted by the medical community in Europe and the United States as clinical meaningful scale to assess visible aesthetic results. The GAIS can be used not only by the Investigator, but is also a useful tool for

Table 3. Global Aesthetic Improvement Scale (GAIS)

Rating (for the CCI)	Description (for the Investigator and CCI)
Very much improved	Optimal cosmetic result for the subject.
Much improved	Marked improvement in appearance from the original condition, but not completely optimal for this subject.
Improved	Obvious improvement in appearance from the original condition.
No change	The appearance is essentially the same as the original condition.

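### The MITT set behind every efficacy analysis requires the week-3 injection, so it discards valid week-3 ratings of randomised subjects who were not injected a second time

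*Combined protocol and SAP*

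**What the plan says.** Section 10.1 of the combined protocol and SAP defines two populations. The Safety set is everyone injected with study product. The MITT set is described as follows: "Includes all treatment compliant subjects, i.e. subjects" treated "at both baseline and 3 weeks". The section then states: "All efficacy analyses will be based on the MITT population". No broader efficacy set and no sensitivity analysis is visible. Section 10.5 presents observed cases without imputation, which does not bring back subjects left out of the set.

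On timing, the schedule of events (section 4.7) places randomisation and the first injection at visit 2. For later treatment visits, section 7.1 says: "At treatment visits, all assessments must be performed before study treatment is administered".

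On subjects who miss the second injection but stay in the study, section 8.1.8 says that after a pregnancy "the subject must be withdrawn from any following study treatment, but should continue to be followed within the study". Section 5.5 agrees: "The subject may remain in the study, but no invasive procedure should be conducted". The schedule of events includes a urine pregnancy test at week 3.

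On purpose, section 2.3 says: "Comparison between the two groups will help to determine if the different treatment approaches affects the outcome, such as subject satisfaction". One objective in section 3.1.1 reads: "To evaluate subject satisfaction treating chin versus treating NLF/ML, respectively, and in combination".

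**The concern.** A modified intention-to-treat set usually trims randomised subjects for reasons settled at or near randomisation. This one adds a condition met three weeks later, after the first injection has had its effect and after the week-3 ratings are complete. Despite its name, it is a set of subjects who completed both treatment sessions.

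The area treated first differs by group. An adverse event or disappointment after the first session could lead to no second session, and this could happen more often in one group. The two groups would then no longer be the groups that were randomised. Percentages by group, which section 10.3 plans, are affected by this just as a formal comparison would be. Section 2.3 intends the results to inform treatment guidelines.

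The loss matters most at week 3. That is the only visit at which one group has had the chin alone and the other the folds and lines alone, so it is where the objective of comparing the two areas is answered. A second injection is not needed to interpret that result. Item 1 of the satisfaction questionnaire (Appendix 9) concerns the first treatment only and, under the Subject Satisfaction Questionnaire section, is asked at week 3.

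A smaller point is that section 10.1 equates treatment compliance with two sessions, while section 6.5.6 defines it as enough product injected for optimal correction. One term has two meanings.

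**Working it through.** **Order of events, from the documents**

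1. Visit 2: randomisation, then first injection (section 4.7).
2. Visit 3, week 3: GAIS, naturalness and satisfaction are rated (sections 4.7 and 4.8.3).
3. Same visit, after the ratings: second injection (section 7.1 and the treatment footnote to the schedule).
4. MITT membership is settled only at step 3 (section 10.1).

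A subject who reaches step 2 but not step 3 therefore has a week-3 rating and is outside every efficacy analysis. If the subject stays in follow-up, as section 8.1.8 provides after a pregnancy, the week-6 and week-9 ratings are lost too. A subject who leaves before week 3 has no week-3 rating to lose and is not part of this point.

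**Plan's own figure.** There is none to reproduce. Section 10.8 says that the sample size of about 60 (30 per group) is not calculated. No response rate or dropout rate is given.

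**Illustration.** Take n = 30 per group (section 10.8). Assume r improved at week 3 and k subjects dropped from one group only. The values of r and k are assumptions.

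- Rate with everyone kept: r/30.
- If all k dropped are non-improved: r/(30 - k).
- If all k dropped are improved: (r - k)/(30 - k).

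| Rate with all kept | k | All dropped non-improved | All dropped improved |
|---|---|---|---|
| 18/30 = 60.0% | 1 | 18/29 = 62.1% (+2.1) | 17/29 = 58.6% (-1.4) |
| | 4 | 18/26 = 69.2% (+9.2) | 14/26 = 53.8% (-6.2) |
| 24/30 = 80.0% | 1 | 24/29 = 82.8% (+2.8) | 23/29 = 79.3% (-0.7) |
| | 2 | 24/28 = 85.7% (+5.7) | 22/28 = 78.6% (-1.4) |
| | 3 | 24/27 = 88.9% (+8.9) | 21/27 = 77.8% (-2.2) |
| | 4 | 24/26 = 92.3% (+12.3) | 20/26 = 76.9% (-3.1) |
| 27/30 = 90.0% | 1 | 27/29 = 93.1% (+3.1) | 26/29 = 89.7% (-0.3) |
| | 3 | 27/27 = 100% (+10.0) | 24/27 = 88.9% (-1.1) |
| | 4 | not possible (only 3 non-improved) | 23/26 = 88.5% (-1.5) |

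With k = 0 the shift is 0. If both groups start from 24/30 and each loses two non-improved subjects, both show 24/28 and the difference is 0. If each group loses k subjects with opposite outcomes, the spurious difference is r/(30 - k) - (r - k)/(30 - k) = k/(30 - k): 1/29 = 3.4, 2/28 = 7.1 and 3/27 = 11.1 points for k = 1, 2 and 3. The sign depends on which group loses whom.

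**The case against.** The strongest reply is that few subjects will be affected. The week-3 injection is scheduled for everyone whatever the rating; only the week-6 touch-up is optional. Pregnancy is the one route the protocol spells out that leaves a subject untreated but still followed. It would have to be detected in roughly a three-week window among women using birth control, in a study with at least 20 men among about 60 subjects, and it has no evident link to outcome or to injection order. The +12.3-point case needs 4 of 30 subjects (13%) in one group to be rated, not injected and all non-improved, with none lost in the other.

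This stands as far as size goes. The upper values mark what is arithmetically possible and are not a forecast. It does not remove the defect, because section 5.5 also allows discontinuation for safety or by the subject's choice, with a full assessment where possible. Those reasons can be related to outcome.

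A second reply is that the visible analyses are descriptive. That is true, and the synopsis entry on statistical method is blacked out, so no effect on a particular test can be claimed. Descriptive rates shift all the same.

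Third, a fixed twice-treated cohort has a purpose. It keeps weeks 3, 6 and 9 comparable within the same people and suits the combination objective and questionnaire item 2. This is a fair argument for keeping the set at weeks 6 and 9, though not for applying it at week 3.

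Fourth, sections 10.1 and 10.7 already report set sizes, withdrawals and deviations. Those counts do not restore ratings. A subject who stops treatment but stays in the study is not withdrawn and may not appear in the withdrawal listing.

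Enrolling additional subjects, as section 5.5 allows, would restore numbers but not undo the selection.

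**Conclusion.** The point holds. Section 10.1 conditions all efficacy results on an event after randomisation and after the first rating, and it discards week-3 data that are valid for the comparison the study sets out to make. The reading of the text is firm. The consequence is not: the documents fix neither the direction nor the size of any bias, and there is none if every rated subject receives the second injection. Under the assumptions above (30 per group, 60% to 90% improved, 1 to 4 dropped from one group), one group's rate could move by between -6.2 and +12.3 points; a single dropped subject moves it by between -1.4 and +3.1.

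The double meaning of compliance is a minor wording matter. The wording of section 10.1 suggests that two sessions decide membership. If section 6.5.6 decided it instead, selection would depend on the judged treatment result. Overall this is a cheap improvement and not a threat to the study.

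**What to change.** In section 10.1:

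- Define the efficacy set as all randomised subjects injected at baseline, analysed in the group to which they were randomised, with all observed data at weeks 3, 6 and 9.
- Remove the reference to treatment compliance from the definition, so that it no longer conflicts with section 6.5.6.
- Keep subjects treated at both sessions as a supportive set for the combination results at weeks 6 and 9.
- Report by group how many subjects fall outside that supportive set, with reasons.

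A line counting missing ratings as not improved is optional.

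The cost is a few lines of text, one supportive set of week-6 and week-9 tables and one count by group. The one drawback is that a few subjects without the second area treated would slightly dilute the main week-6 and week-9 summaries, which the supportive set covers.
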